### Research Background

Low patient engagement in care and ineffective patient-provider communication are 2 major contributors to health care disparities [1-6]. Minoritized patients are less likely to be engaged in care, particularly in mental health care [5-7], which often leads to lower health service use [8-10], higher treatment dropout rates [5,11,12], and worse clinical outcomes [13]. Reasons for low engagement in mental health care vary but include perceived futility of treatment, inadequate access to care, lack of culturally sensitive treatment, low self-efficacy, and lack of trust in health care systems [14-16]. Minoritized patients are also more likely to experience poor patient-provider communication [1,17] and be excluded from treatment decisions [18]. Studies have found patient-provider interactions to be marked by conflicts, perceptions of discrimination, and provider dominance [18]. Ineffective patient-provider communication perpetuates racial health care disparities by contributing to poor care experiences [19-21], low treatment adherence [22], and negative health outcomes [23].

### PARTNER-MH Intervention

PARTNER-MH incorporates peer support and patient navigation care models to deliver a manualized patient activation, engagement, and communication intervention to racially and ethnically minoritized Veterans in VHA outpatient mental health clinics. The aims of PARTNER-MH are as follows: (1) to engage racially and ethnically minoritized patients in mental health care, (2) to increase patient activation by giving patients the tools to become active

collaborators in their care, and (3) to improve patients' communication skills and participation in shared treatment decision-making.

#### Study Objectives

Aim 1 (primary aim) is to assess the feasibility and acceptability of PARTNER-MH in a VHA mental health care setting.

Aim 2 is to evaluate the preliminary effects of PARTNER-MH on patient activation, patient engagement, and shared decision-making (SDM). We hypothesize that patients randomized to the PARTNER-MH intervention group will report greater patient engagement, patient activation, and SDM than patients randomized to the control group.

Aim 3 is to examine patient-perceived barriers to and facilitators of engagement in PARTNER-MH as well as contextual factors, using the Consolidated Framework for Implementation Research (CFIR) [32], that may inhibit or promote the integration, sustainability, and scalability of PARTNER-MH.

#### Methods

##### Design Overview

This pilot study used a convergent mixed methods design [33] that involved a randomized controlled trial comparing the PARTNER-MH intervention with a wait-list control group with a sample of 50 racially and ethnically minoritized Veterans. The wait-list design was selected as a comparator for treatment as usual because it provides patients with the opportunity to participate in the intervention after the wait period, which facilitates recruitment into the study.

##### PARTNER-MH Interventionists

The interventionists for this pilot study are 2 certified VHA peer support specialists, selected through usual VHA hiring practices and assigned to the mental health service line, who have completed the PARTNER-MH training program. The training program consists of 40 hours of didactic sessions that cover topics such as patient navigation, patient engagement, social determinants of health, diversity and racial discrimination in health care, effective communication, and professional development.

### Adherence to Intervention Protocol

Fidelity assessment was conducted quarterly using a sample of 8 patients in the active group (8/29, 28%) stratified by 2 peers. A total of 2 clinical psychologists from the study team used the PARTNER-MH fidelity 17-item checklist and audio-recorded intervention sessions or conducted live participant observations to assess fidelity. Fidelity assessment outcomes were then discussed with peers as well as the steps needed to reinforce or correct deviations from study procedures. In addition, peers receive weekly supervision to reinforce training information, address challenges, and provide support (aim 1).

### PARTNER-MH Development and Intervention Structure

PARTNER-MH is a theory-driven, peer-led intervention that was developed using participatory approaches [34,35] guided by the CFIR [32]. Specifically, this process involved the active participation of racially diverse Veterans, peers, and peer supervisors throughout the development and pre-implementation phases of PARTNER-MH [36].

PARTNER-MH is a 6-month intervention that consists of individualized sessions with an assigned peer. Sessions are delivered in person, over the phone, or via videoconferencing, depending on patient preferences. Owing to the COVID-19 pandemic and restrictions on in-person visits, most of the sessions were delivered via telehealth. The PARTNER-MH sessions were delivered weekly for the first month, biweekly for the second and third months, and monthly thereafter. Peers and patients also met more often, as needed. The sessions lasted approximately an hour and were tailored to meet patient goals and needs related to engagement, access to services, care coordination, health care communication, and personal support. Peers used the PARTNER-MH handbook to guide and organize their sessions, but they also had the flexibility to use their lived experiences and training to inform the sessions. The flexibility of the PARTNER-MH structure also allowed patients to cover different modules at their own pace. Textbox 1 depicts the modules covered in the handbook and during the sessions.

### Participants and Setting

PARTNER-MH was offered to racially and ethnically minoritized Veterans receiving mental health services from an outpatient mental health clinic at a large VHA medical center in the Midwest and associated community-based outpatient clinics. The program targeted Veterans

across psychiatric diagnostic categories who were relatively new to the broad array but somewhat complicated configuration of VHA outpatient mental health clinics, often requiring help to navigate mental health services. To be eligible for the study, participants must (1) belong to a racially or ethnically minoritized group, (2) be aged  $\geq 18$  years, and (3) have a new medication management or therapy appointment scheduled within 12 months before enrollment in the study or have recently re-established treatment after an absence of 2 years. Veterans are excluded if they (1) have mental or cognitive impairments that limited their ability to give consent (eg, having acute psychotic symptoms or being cognitively impaired during the consent or interview process), (2) have hearing difficulties that prevent participation in the interviews, or (3) received medication management services at the clinic for  $>12$  months before enrollment in the study.

#### Recruitment

Participant recruitment for PARTNER-MH is complete. Multiple strategies were used to recruit participants to capture a diverse group of racially and ethnically minoritized patients. They included inviting eligible patients identified through electronic health records and sending them an introductory letter informing them about the study. The letter gave the participants a method for opting out of further contact. In the absence of such notification, 10 days after the letter's receipt was expected, study staff called the patient to explain the study in greater detail, conduct initial screening, and ask eligible patients whether they wished to participate. Other recruitment strategies included clinician referrals, patient self-referrals, direct advertisements, and snowball sampling (ie, asking enrolled participants to refer others). All eligible patients were given a research packet that included an invitation letter and a study information sheet.

#### Ethical Considerations

Approval was obtained from the Indiana University Institutional Review Board in November 2017 (1708628270) and the Veterans Affairs (VA) Research and Development review committee. Protocol modifications will undergo further review by the institutional review board, be communicated to the research team, and updated in the clinical trials registry.

### Randomization and Protection Against Sources of Bias

Participants completed baseline assessment before being randomized into the study arms to ensure balance and reduce selection bias. Allocation to the treatment arm was carried out using a computer-generated randomization list with randomly varying block sizes of 4 and 8 to maximize allocation concealment. Furthermore, although blinding was not feasible for this project because of the study's limited staffing and the need to collect participant feedback on the feasibility and acceptability of the intervention, study personnel involved in screening and enrollment were masked to the computer-generated randomization assignment and were not included in delivering the intervention. Moreover, peers were not involved in data collection and did not have access to participants' assessment results.

### Wait-list Control Structure and Overview

Participants in the wait-list control group received regular VHA mental health services (eg, individual or group psychotherapy, consults, and medication management) for the 6 months after enrollment. To overcome potential issues of contamination, where a peer could deliver PARTNER-MH services to control group participants, participants in the control group were encouraged not to use peer services unless they dropped out of the study. Chart reviews were conducted to assess contamination.

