### Data Collection Methods, Data Management, and Monitoring

The data collection for this study is ongoing. Screening, enrollment, and survey data were collected and stored via VA REDCap (Research Electronic Data Capture; Vanderbilt University), behind the VA firewall. Outcomes were assessed over the phone at baseline and at 3, 6 (primary end point), 9, and 12 months. Outcome data also included qualitative interviews to evaluate participants' experience of the intervention and organizational factors that may impact its future implementation and the integration of the quantitative and qualitative data. Study participants were compensated with a US \$35 gift card for each assessment except for the primary end point (at 6 months), for which they received a US \$50 gift card. In addition, because of the COVID-19 in-person visit restrictions, participants received a US \$10 gift card for each month they remained enrolled in the study to facilitate access to telehealth delivery of the intervention and retention. A brief exit survey was sent to participants who discontinued the

study to evaluate their experiences in the program. Participants' enrollment in the study was recorded in their medical records, which peers had access to. A data safety and monitoring board was also established to evaluate the data quality and safety of the study.

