#### *Planned Statistical Analyses for Aim 2*

Power calculations are provided, but as a pilot, this study is powered only to detect large differences between groups. With a sample of 22 participants in the intervention group and 15 in the wait-list control group, we have 80% power at a .05 significance level to detect an effect size of 0.965 for tests between groups using 2-sided 2-sample *t* tests. With an estimated SD of 14 for PAM-MH based on previous studies, this sample size will allow detection of a PAM-MH difference of 13.5 between the 2 groups. Within the intervention group, the study can detect an effect size of 0.626 for tests between time points using 2-sided paired *t* tests, for a difference of 8.8 for PAM-MH changes. Similarly, in the wait-list control group, the study can detect an effect size of 0.778 and a difference of 10.8 for PAM-MH changes. To account for 25% attrition during follow-up, the study enrolled 30 intervention participants and 20 wait-list control participants. Figure 2 shows the participant flow.

The internal consistency of each scale for primary and secondary outcomes will be verified in this study sample using Cronbach  $\alpha$ . Distributions of the scale scores will be examined to determine whether transformation of the data or nonparametric tests are required for the analyses. In this study, 2-sample *t* tests and Fisher exact tests for continuous and categorical variables, respectively, will be used to compare the demographic and baseline data between participants with and without complete data. Repeated measures ANOVA (RMANOVA) for the scale scores will be used to compare data among the assessments over time. The RMANOVAs will allow different correlations between each assessment time and will allow for the appropriate covariance structure to model the intraparticipant correlations; they will also include a random effect for peers to account for correlation among participants with the same peer. In this intent-to-treat analysis, the RMANOVAs will provide unbiased estimates under the missing-at-random assumption. A 5% significance level will be used for each test.

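### During the wait, leaving the study is the only stated exception to the request that controls avoid peer services, and no planned analysis examines whether the resulting control dropout departs from missing at random

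*Combined protocol and SAP*

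**What the plan says.** Under Wait-list Control Structure and Overview, controls receive regular VHA mental health services for 6 months. The section gives its reason for restricting peer contact: "To overcome potential issues of contamination, where a peer could deliver PARTNER-MH services to control group participants". The rule that follows is that "participants in the control group were encouraged not to use peer services unless they dropped out of the study", and it adds: "Chart reviews were conducted to assess contamination". It does not say how the chart-review findings enter the analysis.

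Design Overview explains the wait-list choice in part because "it provides patients with the opportunity to participate in the intervention after the wait period".

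Data Collection Methods, Data Management, and Monitoring sets the schedule: "Outcomes were assessed over the phone at baseline and at 3, 6 (primary end point), 9, and 12 months". On discontinuation it says: "A brief exit survey was sent to participants who discontinued the" study, to learn about their experience. It states no further outcome assessment for these participants. The same section describes gift cards for each assessment and for each month enrolled.

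Planned Statistical Analyses for Aim 2 allows for 25% attrition, describes the repeated measures analysis as intent-to-treat, and says that "the RMANOVAs will provide unbiased estimates under the missing-at-random assumption". The one check on missing data compares demographic and baseline characteristics of participants with and without complete data. No sensitivity analysis under missing not at random is described.

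**The concern.** Missing at random holds if, given the scores already observed, dropout does not depend on the scores that go unseen. The control-arm rule gives some ground to doubt this. It attaches one particular consequence to leaving, release from the request to avoid peers, and does so in one arm only. A control who acts on it is someone who wants peer support before the wait ends. That wish may reflect worsening need or rising readiness to seek help. Either could have developed since the last assessment, and either is close to what the Aim 2 measures capture.

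If such controls leave and their 6-month scores are not collected, the model fills the gap from controls with similar earlier scores who stayed. The control mean, and with it the between-arm contrast at the primary end point, could be off. A baseline comparison of completers and non-completers would not show this, because the selection would run through later values that nobody recorded.

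**Working it through.** **The plan's own figures (Planned Statistical Analyses for Aim 2).** Inputs: 22 intervention and 15 control participants analysed, two-sided 5% level, 80% power, PAM-MH SD 14, 25% attrition.
- A two-sample t test (noncentral t) gives a detectable effect of 0.965, and 0.965 × 14 = 13.5 points. Both match the plan.
- 22/0.75 = 29.3, rounded up to 30; 15/0.75 = 20. Both match the plan.
- Standard error of the difference: 14 × √(1/22 + 1/15) = 4.69 points.

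**Bias formula.** Let f be the fraction of controls who leave for this reason. Let D be the points by which their true 6-month mean exceeds the model's prediction. Taking the intervention arm as correctly modelled, the bias in the difference (intervention minus control) is f × D.

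**Assumed inputs.** The documents give neither f nor D. The lower case takes 2 of 20 controls. The upper case takes all 5 of the 20 expected to be lost at 25% attrition. D is set at 7 points (0.5 SD) and 14 points (1 SD).

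| Controls leaving for this reason | f | Bias at D = 7 | Bias at D = 14 |
|---|---|---|---|
| 2 of 20 | 0.10 | 0.7 | 1.4 |
| 5 of 20 | 0.25 | 1.75 | 3.5 |

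The range of 0.7 to 3.5 points is 0.7/4.69 = 0.15 to 3.5/4.69 = 0.75 standard errors, or 0.7/13.5 = 5% to 3.5/13.5 = 26% of the detectable difference.

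**Effect on the test (t-test approximation).**
- At a bias of 1.75 points, the two-sided type I error goes from 5% to 6.5%. Power at a true difference of 13.5 goes from 80% to 68% if the bias is toward the null, or to 89% if away from it.
- At a bias of 3.5 points, the type I error is 11.2% and power is 55% or 94%.

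**When bias arises.** A simulation assumed 25% control dropout and within-person correlation of 0.3 to 0.7. It estimated the 6-month control mean by regression on baseline and 3-month scores.
- Dropout depending on the observed 3-month score: bias of about 0.0.
- Dropout depending on the unobserved 6-month score, at log-odds of 0.5 to 1 per SD: the control mean shifts by about 0.7 to 2.6 points, with its sign following the direction of selection.

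**Direction.** If leavers do worse than predicted, the control mean is too high and the effect is understated. If they do better, the effect is overstated. The documents do not settle which applies.

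**The case against.** The strongest reply is that the rule is much milder than it first appears. Controls were encouraged, not forbidden. The exception can be read simply as saying that people who have left are no longer bound by the request. They kept their usual psychotherapy, consults and medication management, and could have the intervention once the wait ended. Gift cards of US $35 per assessment, US $50 at 6 months and US $10 per month enrolled all favour staying. The statement about missing at random is conditional and, as worded, correct. All of this stands, and it lowers the likely number of such departures.

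A reader might infer that the rule makes dropping out the way to obtain peer care, or that it pushes controls out. The text does not support that: it states an exception and offers no inducement. A reader might also infer that controls who leave are not assessed. The documents are silent beyond the exit survey, and they refer to a published protocol paper that is not available here. The fair statement is that continued assessment is not stated.

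The upper figure of 3.5 points is also generous. It needs all five expected control losses to be of this kind, although the 25% is general attrition applied to both arms. It also needs an average departure of 14 points after conditioning on earlier scores. Conditioning on a single earlier score with correlation 0.5 to 0.7 (assumed), the residual SD is 14 × √(1 − 0.25) = 12.1 to 14 × √(1 − 0.49) = 10.0. A 14-point departure therefore exceeds one residual SD on average.

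What remains is that the rule applies to one arm, concerns the period before the primary end point, and is paired with a check that cannot detect the problem it might cause.

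**Conclusion.** The point holds as a possibility, at minor severity. The plan gives controls a reason to leave that may be related to the Aim 2 outcomes, states no outcome assessment after discontinuation beyond an exit survey, and has no analysis that examines departures from missing at random. The 6-month contrast may be biased in either direction. If dropout is explained by observed scores, there is no bias.

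The illustrative 0.7 to 3.5 points rests on assumed values for how many controls leave for this reason and how far they depart from prediction, and on a correctly modelled intervention arm. It is below one standard error throughout, though its upper end would matter for a test at the 5% level. The documents do not support saying that the contrast is biased or that the intent-to-treat label is false.

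The severity is minor because feasibility and acceptability are the primary aim, while this contrast estimates preliminary effects in a pilot that the plan itself says can detect only large differences.

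**What to change.** Leave the care advice unchanged and amend the follow-up and analysis rules.

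1. For assessments still pending, separate use of peer services from study exit. Controls who use peers stay in the phone assessments and are analysed as randomised; only withdrawal of consent ends assessment.
2. Use the existing chart review and exit survey to report peer-service use and reasons for dropout by arm.
3. Add a sensitivity analysis that shifts the missing 6-month control values in both directions, for example by 0, ±5 and ±10 PAM-MH points. With 5 of 20 missing, these shifts move the control mean by 0.25 × 5 = 1.25 and 0.25 × 10 = 2.5 points. Report the shift at which the conclusion changes, and present the main result as conditional on missing at random.

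The cost is a few extra calls with the usual gift cards and one sensitivity table. Keeping controls who used peers in the comparison may dilute the contrast slightly. The reach of item 1 is limited: recruitment is complete, so it helps only 6-month assessments not yet done, and the rule has little bearing once the wait is over. Items 2 and 3 can be done whatever the stage of follow-up; item 3 needs no new data.

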### Data Collection Methods, Data Management, and Monitoring

The data collection for this study is ongoing. Screening, enrollment, and survey data were collected and stored via VA REDCap (Research Electronic Data Capture; Vanderbilt University), behind the VA firewall. Outcomes were assessed over the phone at baseline and at 3, 6 (primary end point), 9, and 12 months. Outcome data also included qualitative interviews to evaluate participants' experience of the intervention and organizational factors that may impact its future implementation and the integration of the quantitative and qualitative data. Study participants were compensated with a US \$35 gift card for each assessment except for the primary end point (at 6 months), for which they received a US \$50 gift card. In addition, because of the COVID-19 in-person visit restrictions, participants received a US \$10 gift card for each month they remained enrolled in the study to facilitate access to telehealth delivery of the intervention and retention. A brief exit survey was sent to participants who discontinued the

study to evaluate their experiences in the program. Participants' enrollment in the study was recorded in their medical records, which peers had access to. A data safety and monitoring board was also established to evaluate the data quality and safety of the study.

#### [Aim 1 Outcomes](#)

Aim 1 is to assess the feasibility and acceptability of PARTNER-MH in a VHA mental health care setting.

The feasibility of PARTNER-MH will be determined based on participants' recruitment, enrollment, and retention rates. Program acceptability for participants will be evaluated using session attendance, number of contacts with peer navigators, and the Patient Satisfaction Survey, which is an 11-item questionnaire rated on a 3-point Likert scale ranging from 1 (not at all) to 3 (very). Satisfaction with the peer was evaluated using a survey that included questions about the patient's relationship with the peer and views of support provided by the peer.

Descriptive summaries of recruitment, enrollment, retention, and satisfaction rates will be reported. Participant feedback from qualitative interviews will also be used to inform the feasibility and acceptability of PARTNER-MH (aim 3).

